POCUS has been shown to be a promising technique to measure skeletal muscle mass [12]. It is non-invasive, can be performed at the bedside and has an excellent intra-class correlation coefficient for intra- and inter-observer agreement. [13, 14] Recent studies in a subgroup of hospitalized patients have shown that Qcsa measurements can predict readmission and mortality [15, 16]. ED data however are scarce: Shah et al found in a subset of elderly trauma patients that ultrasound measurements of biceps and quadriceps had modest concordance with the Clinical Frailty Scale (CFS9) [17], whereas Benton et al demonstrated that ultrasound measurements of sarcopenia in older non-trauma patients were (to a variable extend) associated with frailty, falls and subsequent hospitalizations [18].

As POCUS measurement of Qcsa is independent of patient effort and functional or cognitive impairment, it has the potential to be a valuable (alternative) screening tool for functional decline

and mortality in older patients in the ED. However, until now, no data have been published about the relation between Qcsa and functional outcome for patients presenting in the ED.

The aim of this study is to evaluate whether ultrasound measurements of the Qcsa in the ED may be utilized to identify older patients who are at risk for functional decline, ED revisit or death. Our study hypothesis is that Qcsa measurements can predict functional decline, ED revisit or death of older ED patients.

- **Research question**

Primary objective

To evaluate:

- The relation between POCUS measurements of the Qcsa in patients >70 presenting in the ED and ED revisit or death within three months and functional decline within twelve months of their ED visit. Functional decline in this respect is defined as at least one point increase in the Katz ADL-6 survey score or new institutionalization (higher level of assisted living) within twelve months after ED visit.

Secondary objectives

To evaluate:

- To compare the ability of the Qcsa ultrasound to predict functional decline, ED revisit or death in older patients in the ED to the APOP questionnaire (gold standard).
- To compare the added value of Qcsa ultrasound to the APOP questionnaire in the prediction of functional decline, ED revisit or death in older patients in the ED.
- To evaluate the relation between Qcsa ultrasound and physical activity (as scored by KATZ ADL-6 questionnaire).

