## 5.9 Data analysis

 
Justification of sample size (e.g. power analysis)
 

The sample size is calculated based on functional decline and mortality in elderly visiting the ED. We defined functional decline as at least one point increase in the Katz ADL-6 survey score or new institutionalization (higher level of assisted living) within twelve months after ED visit. Prior research in the Netherlands found 9,5% of patients aged <math>\geq 70</math> year died within three months after ED visit and 30,6% experienced functional decline or mortality at 90-day follow-up [8]. With an assumed prevalence of the composed endpoint of 30%, 54 patients are needed to be able to confirm a diagnostic test accuracy with a sensitivity and specificity of <math>>0.8</math> each for a predefined Qcsa cut-off value with a power of 90% and an alfa error of 0.05. To allow for loss of follow-up, 25% more patients will be recruited, resulting in a sample size of 68 patients.

 
Statistical analysis
 

Continuous variables are expressed as mean (95% CI) when normally distributed and median with interquartile range when not normally distributed. Categorical data are presented as absolute

numbers and percentages.

There is a difference in muscle mass between man and woman. The ultrasound measured Qcsa will therefore be adjusted for sex by multiplying female Qcsa with the coefficient 1.484 (male=1) prior to analysis [15]. Diagnostic accuracy of QCSA will be presented as sensitivity and specificity of the optimum Qcsa cut-off point to separate cases (primary endpoint reached after three or twelve months) from non-cases. This optimum cut-off point is calculated as the maximum sum of sensitivity + (1-specificity) using ROC statistics (under the condition of equal costs of misqualification).

A logistic regression model will be used to evaluate whether individual Qcsa predicts functional decline, ED revisit or death. Age, comorbidity, Katz ADL-6, known dementia are defined as clinically relevant covariates and will be included in the regression model.. The predictive ability of the multivariable risk prediction models (e.g. Qcsa prediction model vs APOP prediction model) will be compared.  $\chi^2$  values will be calculated for each prediction model.

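### The cut-off rule in section 5.9 has a sign error: maximising sensitivity + (1 − specificity) always ends with every patient called at risk

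*Combined protocol and SAP*

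**What the plan says.** The statistical analysis part of section 5.9 announces the diagnostic accuracy result: "Diagnostic accuracy of QCSA will be presented as sensitivity and specificity of the optimum Qcsa cut-off point". The cut-off is meant "to separate cases (primary endpoint reached after three or twelve months) from non-cases". The rule that picks it is "This optimum cut-off point is calculated as the maximum sum of sensitivity + (1-specificity) using ROC statistics", qualified in parentheses by "under the condition of equal costs of misqualification".

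The sample size paragraph in the same section aims to confirm sensitivity and specificity above 0.8 each. It starts from this assumption: "With an assumed prevalence of the composed endpoint of 30%, 54 patients are needed". It also refers to a Qcsa cut-off fixed in advance, but gives no value. The study aim in section 4 is to learn whether Qcsa measurements "may be utilized to identify older patients who are at risk for functional decline, ED revisit or death". No other cut-off rule appears anywhere in the document.

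**The concern.** The usual rule for two equally weighted error rates is the Youden index, sensitivity + specificity − 1, which equals sensitivity **minus** (1 − specificity). The plan has a plus sign there. With the plus sign, false positives count in favour of a cut-off, so the rule rewards flagging more people without limit. The word for addition stands beside the symbol in the text, so a PDF reading fault is an unlikely explanation.

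Sensitivity and specificity at this cut-off are the planned accuracy result, and they are the quantities on which the sample size is justified. If the rule is followed as written, that result carries no information about Qcsa. If an analyst notices and substitutes another rule, the choice is made with the data in hand, and the plan no longer pre-specifies it.

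**Working it through.** **Inputs.** 54 evaluable patients and 30% prevalence, both from the sample size paragraph of section 5.9. 54 × 0.30 = 16.2, taken as 16 cases and 38 non-cases. These figures serve only to put counts on the result. The plan states no cut-off or expected score that could be reproduced first.

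**Score as written.** Order patients by Qcsa and call the k patients with the lowest values at risk, k = 0 to 54. The score is

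S(k) = Se + (1 − Sp) = (cases flagged)/16 + (non-cases flagged)/38.

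**Step from k to k + 1.** The score rises by 1/16 = 0.0625 if the next patient is a case, or by 1/38 = 0.0263 if a non-case. It never falls. The maximum is therefore at k = 54: S = 1 + 1 = 2, with Se = 1, Sp = 0 and Youden index 1 + 0 − 1 = 0. Misclassified: 38/54 = 70.4%.

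**If the all-positive end point is barred** (and Qcsa values are not tied), the maximum moves to k = 53:

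| Patient left unflagged | Se | Sp | S | Misclassified |
|---|---|---|---|---|
| Non-case | 1 | 1/38 = 0.026 | 1.974 | 37/54 = 69% |
| Case | 15/16 = 0.9375 | 0 | 1.9375 | 39/54 = 72% |

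**Comparison with good cut-offs.**

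| Cut-off | Se | Sp | Written score | Youden index |
|---|---|---|---|---|
| Perfect separation | 1 | 1 | 1 + 0 = 1.0 | 1.0 |
| 0.8 for each | 0.8 | 0.8 | 0.8 + 0.2 = 1.0 | 0.6 |
| Everyone flagged | 1 | 0 | 1 + 1 = 2.0 | 0 |

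The written rule prefers flagging everyone to perfect separation by 2.0 to 1.0.

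**Other prevalences.** The true prevalence may differ from 30%. Assuming 40% or 50%, flagging everyone misclassifies 32/54 = 59% or 27/54 = 50%. Sensitivity 1 and specificity 0 hold at any prevalence.

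**Simulation check.** Normally distributed data, 30% cases, 54 or 68 patients, AUC 0.50, 0.71, 0.88 and 0.98, 3,000 datasets per setting. The written rule gave 1.000/0.000 in every dataset. With the end point barred, specificity never exceeded 0.026 at 54 patients or 0.021 at 68. The Youden rule on the same model at 54 patients gave mean apparent sensitivity/specificity of 0.61/0.56, 0.74/0.69, 0.85/0.83 and 0.96/0.95, so it responds to the data.

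**Why the repair must be written down.** The equal-costs parenthesis has two readings: equal weight on the two error rates (Youden), or equal cost per misclassified patient (maximise prevalence × Se + (1 − prevalence) × Sp). Under an assumed equal-variance normal model with separation d, the second reading shifts the cut-off by ln(0.7/0.3)/d = 0.847/d from the Youden point:

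| AUC | d | Youden Se/Sp | Per-patient cost Se/Sp |
|---|---|---|---|
| 0.883 | 1.683 | 0.80/0.80 | 0.63/0.91 |
| 0.75 | 0.954 | 0.68/0.68 | 0.34/0.91 |

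The two repairs would report clearly different accuracy.

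**The case against.** The best defence is that this is a drafting slip with recoverable intent. The text speaks of an optimum, of separating cases from non-cases, of ROC statistics and of equal costs, and the sample size paragraph wants specificity above 0.8. A specificity of 0 contradicts all of that. Standard Youden software would not produce it, and a competent analyst would probably notice. The primary objective concerns the relation between Qcsa and outcome, which the regression addresses ("A logistic regression model will be used to evaluate whether individual Qcsa predicts functional decline, ED revisit or death"), and that analysis does not use the cut-off.

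Most of this is right and limits the reach of the problem. It does not remove it. The intent has to be inferred, the equal-costs wording leaves two candidate rules, and those rules give different results. The affected output is also the one on which the sample size is justified, so it is not peripheral.

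A second objection is that the corrected rule would still pick a cut-off from the same patients in whom accuracy is reported. That is optimistic (apparent 0.61/0.56 when the true AUC is 0.50), and it sits badly with the pre-set cut-off mentioned in the sample size paragraph. Both observations are correct. They are separate issues that correcting the sign does not settle, and they are no reason to leave the formula as it is.

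**Conclusion.** The concern holds and should be fixed before analysis. Followed as written, the rule returns sensitivity 1 and specificity 0 for any data, or at best one patient short of that if the end point is excluded and there are no ties. This is algebra and rests on no assumption about Qcsa. The 70% misclassified (38 of 54) does rest on the plan's 30% prevalence. It would be 59% or 50% at an assumed 40% or 50%. The likely cause is a wrong sign in the Youden index. The damage is confined to the cut-off and the accuracy reported at it. The ROC curve, the logistic regression, the Qcsa versus APOP comparison and the planned number of patients do not change.

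**What to change.** Before analysis, replace the sentence in section 5.9 with:

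> The optimum cut-off is the value that maximises the Youden index, sensitivity + specificity − 1 (equivalently sensitivity − (1 − specificity)); equal costs of misclassification means that sensitivity and specificity are weighted equally.

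Only if equal cost per misclassified patient is what the sponsor means, write instead:

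> The optimum cut-off maximises prevalence × sensitivity + (1 − prevalence) × specificity,

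and name the prevalence used.

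The cost is one sentence, with no change to sample size, data collection or budget.

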### 3. ABSTRACT (max. 250 words)

- **Background**

Older people visit the ED more frequently than younger people and have a higher risk of functional decline, ED revisit or death. Several screening tools (such as VMS and APOP) have been developed to identify patients at the highest risk of adverse outcomes. Almost all require adequate communication with the patient, which is not always possible, for example when elderly patients present with a delirium. Point of Care Ultrasonography (POCUS) may be a valuable alternative screening tool in these instances.

- **Main research question**

To identify whether POCUS measurement of the rectus femoris muscle cross-sectional area (Qcsa) can be used as an alternative screening tool to predict functional decline, ED revisit or death in elderly patients in the ED.

- **Design (including population, confounders/outcomes)**

This is a single centre prospective trial. Patients >70 years and older presenting in the ED of the UMCG hospital who are participating in the Acutelines bio-databank are eligible for inclusion. 68 patients will be included. Data will be extracted from the Acutelines bio-databank. A trained physician will perform ultrasound measurements in a standardized way.

- **Expected results**

The aim of this study is to evaluate whether ultrasound measurements of the Qcsa can be utilized to identify older patients who are at risk for functional decline, ED revisit or death.

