A 2-sided P-value <0.05 will be considered statistically significant. Missing data are reported in the results section according to the STROBE 2015 guideline. All statistical analyses will be performed using R or SPSS 26.0 software.

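### The only model said to evaluate whether Qcsa predicts the outcome is covariate-adjusted, so it tests added information, while the hypothesis and the sample size concern Qcsa on its own

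*Combined protocol and SAP*

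**What the plan says.** Section 4 states the hypothesis without any condition: "Our study hypothesis is that Qcsa measurements can predict functional decline, ED revisit or death of older ED patients". Incremental value appears separately, as a secondary objective and against APOP only: "To compare the added value of Qcsa ultrasound to the APOP questionnaire in the prediction of functional decline, ED revisit or death". The abstract gives the reason for wanting a stand-alone measure, namely the limits of existing screening tools: "Almost all require adequate communication with the patient, which is not always possible".

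The statistical analysis in 5.9 has three parts that bear on prediction.

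- **Unadjusted accuracy.** "Diagnostic accuracy of QCSA will be presented as sensitivity and specificity of the optimum Qcsa cut-off point to separate cases". The cut-off is found from the study's own ROC curve. No null value, test or confidence interval is given.
- **Regression.** "A logistic regression model will be used to evaluate whether individual Qcsa predicts functional decline, ED revisit or death". The next sentence fixes its content: "Age, comorbidity, Katz ADL-6, known dementia are defined as clinically relevant covariates and will be included in the regression model". No model with Qcsa alone is described.
- **Model comparison.** "The predictive ability of the multivariable risk prediction models (e.g. Qcsa prediction model vs APOP prediction model) will be compared", with a chi-square value for each model. This serves the APOP objectives.

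A general rule follows: "A 2-sided P-value <0.05 will be considered statistically significant". No statistic is named as the primary test. The sample-size paragraph of 5.9 is built on a different quantity: sensitivity and specificity above 0.8 each at a predefined Qcsa cut-off, with 30% prevalence, 90% power and alpha 0.05.

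**The concern.** The two questions have different null hypotheses. For the stated hypothesis, the null is that Qcsa does not separate cases from non-cases. For the Qcsa coefficient in the planned model, the null is that Qcsa carries nothing beyond age, comorbidity, Katz ADL-6 and dementia.

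The protocol itself gives reason to expect these to diverge. Section 4 says that sarcopenia and frailty overlap in their physical aspects, and it makes the relation between Qcsa and Katz ADL-6 a secondary objective. A measure that works as a screen because it reflects frailty will lose part of its effect once other frailty measures are in the model. For a patient who cannot answer questions, the absence of added information beyond a functional questionnaire says little about whether ultrasound is useful.

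At stake is a false negative. A non-significant adjusted coefficient could be reported as a failure of Qcsa to predict, and the unadjusted result beside it would have no interval or test to set against that reading.

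**Working it through.** **1. The plan's own figures.** 54 × 1.25 = 67.5, which gives the stated 68. The 54 cannot be reproduced because no null value is stated. As an illustration, with a null of 0.5 and a true sensitivity of 0.8, 90% power needs about 66 patients (one-sided, normal approximation) to 94 (two-sided, exact). Whichever null was meant, the calculation concerns Qcsa alone, so its 90% power does not carry over to an adjusted coefficient. Expected cases are 54 × 0.30 = 16.2. With Qcsa and four covariates (at least five slopes) that is 16.2 / 5 = 3.2 events per slope.

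**2. Why the adjusted coefficient differs.** Orient Qcsa so that higher means less muscle. Take Qcsa and one covariate (Katz) as normal with unit variance within outcome groups, case shifts d_q and d_k, and correlation r. The logistic coefficient of Qcsa is

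- alone: d_q
- adjusted for Katz: (d_q − r·d_k) / (1 − r²)

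Stand-alone sensitivity = specificity = 0.70 means d_q = 2 × z(0.70) = 2 × 0.524 = 1.049. Assume r = 0.5 and d_k = 0.8. The adjusted coefficient is (1.049 − 0.40) / 0.75 = 0.865, before any loss of precision. It is exactly zero at d_q = 0.40, where Qcsa alone still has AUC Φ(0.40/√2) = 0.61.

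**3. Simulated power.** From the plan: n = 54, 30% events, two-sided 0.05. Assumed, because the documents give no such values: four covariates, normal within outcome group, one dichotomised as dementia.

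- Moderate scenario: Qcsa correlates 0.3 with Katz and 0.2 with the others; each covariate has a case shift of 0.5 SD.
- Stronger scenario: correlations 0.5 and 0.3; shifts of 0.8 SD for Katz and 0.5 SD for the others.

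Wald test, 4,000 runs per cell:

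| Stand-alone sensitivity = specificity | Unadjusted | Adjusted, moderate | Adjusted, stronger |
|---|---|---|---|
| 0.80 | 100% | 97% | 95% |
| 0.75 | 99% | 92% | 82% |
| 0.70 | 91% | 68% | 48% |

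Likelihood-ratio tests at 0.70 give 93% unadjusted against 74% and 55%. With all 68 evaluable, the Wald figures at 0.70 are 97% against 82% and 63%.

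**4. Sensitivity to assumptions.** The correlation of the covariates with each other also matters, and the runs in the table leave it unreported. Set at 0.2 to 0.3, power at 0.70 is 90 to 92% unadjusted against 69 to 72% (moderate) and 42 to 48% (stronger); at 0.80 it is about 100% against 94 to 97%. Varying it from 0 to 0.5 moves adjusted power at 0.70 from 51% to 78% (moderate) and from 17% to 57% (stronger). If the covariates are unrelated to Qcsa and outcome, the tests nearly agree (90% against 84 to 89%). At the other extreme, a Qcsa with AUC 0.71 to 0.77 acting wholly through Katz (r = 0.7) is detected in 76 to 93% of trials unadjusted and 8 to 9% adjusted.

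**5. What the ROC result can settle.** With 16 cases and 38 non-cases, 13/16 correct gives an exact 95% interval of 0.54 to 0.96 for sensitivity, and 30/38 gives 0.63 to 0.90 for specificity. Point estimates without intervals would hide this width.

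**The case against.** *No rule ties the conclusion to the adjusted p-value.* This is correct. The plan names no test of the coefficient, mentions chi-square values per model, and will report unadjusted sensitivity and specificity. It would overstate the text to say that the adjusted coefficient is the trial's only significance test, because the sample-size paragraph states an alpha of 0.05 for accuracy. The statistical analysis never carries that criterion out, however. Within it, the adjusted model remains the only inferential analysis assigned to the question of whether Qcsa predicts.

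*The loss is small where the trial is designed.* This also stands: at 0.80 it is 3 to 6 points. A Qcsa at 0.70 misses the protocol's own target. It would still predict the outcome, and that is what the hypothesis asserts.

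*Adjustment is legitimate.* It is, as an answer to the question of added information.

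*A reader might infer that the mismatch can also produce a false positive.* The documents do not support that. In the formula above, d_q = 0 gives −0.40 / 0.75 = −0.53: a Qcsa with no stand-alone discrimination is pushed to the wrong sign, with more muscle and worse outcome. In simulation with covariates correlated 0.2 to 0.3, such a Qcsa gave adjusted rejections in 11 to 13% (moderate) and 38 to 46% (stronger) of trials, but at most 0.6% were in the hypothesised direction. Nobody would read the rest as support for the sarcopenia rationale. Rejection in the hypothesised direction would need Katz and Qcsa to act in opposite ways, whereas Section 4 describes frailty as raising risk.

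**Conclusion.** The point holds as a mismatch between hypothesis and analysis, with a risk of a false negative. With 54 evaluable patients and stand-alone accuracy of 0.70, the assumed scenarios cut power from about 91% to roughly 40 to 70%, a loss of about 20 to 50 points. The loss is larger if the covariates are uncorrelated with each other and small at the 0.80 target. The direction follows from the overlap that the protocol describes; the size depends on correlations and shifts that the documents do not give. Two stronger readings go too far: that the trial can err in either direction, and that it is bound to declare Qcsa a failure when the adjusted coefficient is non-significant. This should be corrected before analysis; it does not invalidate the study.

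**What to change.** In 5.9:

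- Name the unadjusted analysis of sex-adjusted Qcsa as primary. Report the AUC with a 95% confidence interval, and sensitivity and specificity with 95% confidence intervals.
- State the null value for sensitivity and specificity and make it consistent with the sample-size criterion. Say which cut-off they refer to, since the sample-size paragraph assumes a predefined one and the analysis derives it from the data. A test of AUC against 0.5 would not be enough by itself: at 0.70 the unadjusted test already succeeds in about 91% of trials, below the stated target of more than 0.8.
- Keep the model with age, comorbidity, Katz ADL-6 and dementia as a secondary analysis, labelled as the information Qcsa adds to known clinical data.
- State that a non-significant adjusted coefficient does not show that Qcsa fails as a stand-alone screen.

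The cost is a few sentences and some extra output from data already planned, with no added procedures. Writing down the null value will also show whether 54 evaluable patients give the stated power, which is a separate question. The small downside is that the headline result makes no claim of independence from known risk factors; the secondary model covers that.

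### The five-parameter logistic model rests on about 16 assumed events with no optimism correction, so its apparent predictive ability is expected to be overstated

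*Combined protocol and SAP*

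**What the plan says.** All of the relevant text is in section 5.9 (Data analysis) of the combined protocol and SAP, except the endpoint definition and objectives, which are in section 4.

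- **Model.** Logistic regression relates Qcsa to functional decline, ED revisit or death. On adjustment: "Age, comorbidity, Katz ADL-6, known dementia are defined as clinically relevant covariates and will be included in the regression model". How comorbidity and Katz ADL-6 are coded is not stated.
- **Comparison.** "The predictive ability of the multivariable risk prediction models (e.g. Qcsa prediction model vs APOP prediction model) will be compared". Chi-square values are to be calculated for each model. The make-up of the APOP model is not given.
- **Sample size.** "With an assumed prevalence of the composed endpoint of 30%, 54 patients are needed". The calculation concerns sensitivity and specificity at a Qcsa cut-off, not the regression model. Adding 25% for loss to follow-up gives 68.
- **Significance.** "A 2-sided P-value <0.05 will be considered statistically significant". The test to be used for the Qcsa coefficient is not named.

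Neither section 5.9 nor any other section mentions penalised estimation, shrinkage, bootstrap, cross-validation or external validation. Section 4 makes two prediction questions secondary objectives: Qcsa compared with APOP, and the value that Qcsa adds to APOP.

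**The concern.** A logistic model fitted by ordinary maximum likelihood to few events per parameter follows chance features of its sample. When its discrimination and fit are then measured in those same patients, they look better than they would in the next patients. The gap grows with the number of parameters and shrinks with the number of events.

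Here the model-based results answer two of the stated objectives. The reported accuracy is what a reader would use to decide whether ultrasound could stand in for a questionnaire when communication is impaired. An AUC that is 0.1 too high could change that judgement.

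**Working it through.** **1. The plan's own figures.** 54 × 1.25 = 67.5, rounded up to 68, so the recruitment target reproduces. The 54 itself cannot be checked strictly, because no null sensitivity or specificity is stated. That is a separate matter. Here 54 and 30% are taken as given.

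**2. Parameters.** Qcsa (1) + age, comorbidity, Katz ADL-6 and known dementia (at least 4) = at least 5, not counting the intercept. Coding comorbidity as four indicators would give 8.

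**3. Events per parameter.**

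| Patients | Event proportion | Events | Per parameter (5) |
|---|---|---|---|
| 54 | 30% | 16.2 | 3.2 |
| 68 | 30% | 20.4 | 4.1 |
| 54 | 50% | 27 | 5.4 |
| 68 | 50% | 34 | 6.8 |

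The 50% rows are an assumption. The plan's 30% rests on a source in which "30,6% experienced functional decline or mortality at 90-day follow-up [8". The study endpoint adds ED revisit and counts functional decline to twelve months, so more events are plausible.

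**4. Size of the optimism.** The documents give no effect sizes, so these are assumed. Set A uses independent normal predictors with odds ratio 1.65 per SD for Qcsa and 1.5 per SD for each of four covariates. Set B uses a Qcsa log-odds ratio of 0.50 (moderate) or 0.80 (strong) per SD, other predictors of similar or smaller size, and dementia in 15%. Each model is fitted by maximum likelihood and then applied to fresh patients.

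| Setting | Apparent AUC | AUC in new patients | Median calibration slope in new patients |
|---|---|---|---|
| A, 54 patients, 30% | 0.79 | 0.68 | 0.52 |
| A, 68 patients, 50% | 0.77 | 0.70 | 0.63 |
| A with 8 parameters, 54 patients, 30% | 0.82 | 0.66 | – |
| B moderate, 54 patients, 30% | 0.755 | 0.634 | 0.42 |
| B strong, 54 patients, 30% | 0.818 | 0.727 | 0.58 |
| B, no predictor has any effect, 54 patients, 30% | 0.68 | 0.50 | 0 |

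A slope of 1 is ideal. A slope near 0.5 means that the predicted log-odds are spread about twice as widely as they should be.

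**5. Qcsa coefficient (54 patients, 30%, set B).** Moderate: mean 0.61 against a true 0.50, and 0.61/0.50 = 1.22; median 0.57, and 0.57/0.50 = 1.14. Strong: mean 1.00 against 0.80, ratio 1.25; median 0.94, ratio 1.18. A set A run gave a median of 0.56 against 0.50, ratio 1.12. The inflation is thus about 12% to 25%, depending on summary and effect size. With a true effect of zero the mean was 0.01, that is, unbiased.

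**6. Type I error for Qcsa (set A, no Qcsa effect, 54 patients).** The likelihood-ratio test rejected in about 7%, the Wald test in 5.0%. With 68 patients the figures were 5.9% and 4.6%.

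**7. What size would support the model.** For expected shrinkage S = 0.9, n = p / [(S − 1) ln(1 − R²/S)]. With p = 5 and an assumed Cox-Snell R² of 0.20: 5 / [−0.1 × ln(1 − 0.2222)] = 5 / 0.0251, about 199. For R² of 0.106 or 0.30 the answers are 400 and 124. The planned sample falls short of each.

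**The case against.** **The event count is probably too low.** This is fair: 16 follows from the plan's assumption and is not a forecast. It changes the size and not the direction. At 34 events the AUC gap in set A is still 0.77 − 0.70 = 0.07.

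**The study was sized for something else.** Also true. The sensitivity and specificity analysis uses Qcsa alone, so this point does not touch it. The covariates are prespecified, so no selection bias is added. The model comparison nevertheless answers stated secondary objectives.

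Three stronger readings are tempting, and the documents do not support them.

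- *The comparison is tilted towards Qcsa.* A reader might infer this by taking APOP as a single score against a five-parameter model. Section 5.9 calls both models multivariable and does not say that APOP enters alone. If both carry the same covariates, the parameter counts can be equal. What stands is conditional: if the models differ in size, uncorrected values favour the larger one.
- *The test of Qcsa exceeds its 5% error rate.* This holds for a likelihood-ratio test and not for a Wald test, and the plan names neither.
- *The Qcsa effect will be overstated.* It is inflated on average only if a true effect exists. At zero effect it is unbiased, and in any single dataset the error may go either way.

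**The remedy is incomplete.** This stands in part. Under moderate effects the bootstrap-corrected AUC averaged 0.663 against 0.638 in new patients, so some optimism remained.

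**Conclusion.** The point holds for discrimination and calibration. As written, the plan will report predictive ability from a model with about 3 to 4 events per parameter on its own assumptions, measured in the patients who were used to fit it. On average the apparent AUC is expected to exceed that in new patients by about 0.09 to 0.12 with 54 patients and 30% events (0.818 − 0.727 and 0.755 − 0.634, with set A between them). With 68 patients and 50% events, the excess is about 0.06 to 0.09. Calibration slopes of roughly 0.4 to 0.6 are expected in the first case.

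These sizes rest on assumed effects, mostly independent predictors and five parameters. The direction does not depend on the particular effect sizes tried. The inflation of the Qcsa coefficient and the excess type I error are secondary and conditional. An advantage for Qcsa over APOP is not shown, because the APOP model is unspecified. This should be corrected before analysis, but it does not undermine the cut-off accuracy analysis.

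**What to change.** In the statistical analysis part of section 5.9:

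1. State how each covariate is coded, with comorbidity entered as one score.
2. Define the Qcsa and APOP models in full, with the same covariates in each.
3. Fit both with one prespecified penalised likelihood, for example Firth, and name the test for Qcsa.
4. Report bootstrap optimism-corrected AUC and calibration slope for each model, repeating the whole fit in every resample.
5. Base the comparison on the corrected values and not on the apparent chi-square values.

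In simulation with 54 patients and 30% events, bootstrap correction of the maximum-likelihood model moved mean AUC from 0.814 to 0.736 (0.735 in new patients) under strong effects, and from 0.760 to 0.663 (0.638 in new patients) under moderate effects. Firth estimation gave a mean Qcsa coefficient of 0.51 against a true 0.50, where maximum likelihood gave 0.62 in that run. The two steps were checked separately, not in combination.

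The cost is revised wording and a little more analysis code in R, which the plan already allows. No further patients or data are needed. Reported accuracy will look less favourable, and the report should say that the correction reduces optimism but may not remove it.
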